Serum or urine pregnancy test (WOCBP only) ^j		≤7			Every 4 weeks		х		Mandatory serum test at screening and EOT. Serum or urine test every 4 weeks during study treatment period.
HBV & HCV serology; HIV test (only required at country level)		x							

Procedure	Pre- screening ^a	Screening ^b	Treatment (Cycle 1	Subseque (14 ±2 da previous	ent Cycles ays from infusion)	End of treatment	Follow-up ^d	Notes
Day(D)	Days prior to initial infusion	Days prior to initial infusion	D1 Pre- infusion	D8	D1 Pre- infusion ^c (±2 days)	Every 8 weeks (±7 days)	D30 after last infusion (±5 days)	D90 after last infusion (±7 days)	
Laboratory assessments ^k		≤7	X/	х	Х		Х		During first 2 cycles, hematology and liver function tests will be assessed weekly.
12-lead ECG		≤7	Х		Х		Х		
Specific ocular test		≤28					Х		Performed by the ophthalmologist include visual acuity, slit-lamp under dilatation, and Schirmer's test at screening, EOT and whenever clinically indicated
Assessment of ocular/visual symptoms ^m		≤28	Х		Х		Х		

Procedure	Pre- screening ^a	Screening ^b	Treatment (Cycle 1	Subseque (14 ±2 da previous	ent Cycles ays from infusion)	End of treatment	Follow-up ^d	Notes
Day(D)	Days prior to initial infusion	Days prior to initial infusion	D1 Pre- infusion	D8	D1 Pre- infusion ^c (±2 days)	Every 8 weeks (±7 days)	D30 after last infusion (±5 days)	D90 after last infusion (±7 days)	
Study intervention			Х		Х				Participants should receive study intervention until documented disease progression, unacceptable toxicity, new anti-cancer therapy initiation, or the participant's or Investigator's decision to stop the treatment, whichever comes first.
AE assessment		Xn	<→						
Concomitant medication review		Х	←===					====→	

Procedure	Pre- screening ^a	Screening ^b	Treatment (Cycle 1	Subseque (14 ±2 da previous	ent Cycles ays from infusion)	End of treatment	Follow-up ^d	Notes
Day(D)	Days prior to initial infusion	Days prior to initial infusion	D1 Pre- infusion	D8	D1 Pre- infusion ^c (±2 days)	Every 8 weeks (±7 days)	D30 after last infusion (±5 days)	D90 after last infusion (±7 days)	
Tumor assessment - RECIST v1.1 - CT/MRI ⁰		≤28				x	Х	Х	Imaging assessments are to be scheduled using the C1D1 date as the reference for all time points and are not to be scheduled based on the date of the previous imaging time point. Please refer to Section 8.1 for further information.
Tusamitamab ravtansine PK			Refer to PK/AT	TA flowchar	t Section 1.3.2				Section 8.4

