8.2.2 Specific ocular tests

Specific complete ocular tests will include: assessment of ocular/visual symptoms and ocular exams.

Ocular/visual symptoms must be assessed by the Investigator at screening, at each visit before study treatment administration (including C1D1), at EOT, and whenever clinically indicated. If any visual symptom is reported, an ophthalmologist visit must be scheduled.

Specific ocular tests performed by the ophthalmologist at screening, at EOT, and whenever indicated will include:

- Visual acuity.
- Slit lamp under dilatation.
- Schirmer's test.

In participants with any ocular/visual symptom (eg, blurred vision, photophobia), complete ocular tests will be repeated at the time of the occurrence of the ocular toxicity, if any, regardless of the grade. Thereafter, visual acuity, slit lamp examination under dilatation, and Schirmer's test will be repeated once weekly (if not recommended to have less frequent assessment by ophthalmologist based on lesion characteristics) until resolution to Grade 1. In case of recurrent ocular toxicity observed in subsequent cycles, visual acuity and slit lamp examination under dilatation, and Schirmer's test will be performed at the time of the event onset, then weekly until resolution to Grade 1. Schirmer's test is mandatory for baseline assessment; it can be omitted from further ocular assessments if not considered a required examination per reported events category (ie, no symptom/findings of dry eye).

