8.2.6.2 Ocular toxicity

• It is recommended that topical artificial tears (and/or hyaluronic ophthalmic gel) are used regularly in all patients treated with tusamitamab ravtansine during the study treatment period.

- The patient should be asked about ocular/visual symptoms at each visit, and ocular evaluation including visual acuity, slit lamp examination under dilatation, and Schirmer's test should be carried out on according to SoA (Section 1.3). Ocular evaluation will be performed at screening, as required during the treatment (ie, on occurrence of ocular symptoms such as blurred vision, photophobia, pain), at the EOT visit, and when relevant at follow-up visit(s). The outcome of the examination should be available before infusion of the next cycle. If ocular symptoms are present, then a formal ocular examination should be performed. In patients with any ocular/visual symptom(s) (eg, blurred vision, photophobia), the ocular evaluation should be repeated once weekly, unless less frequent assessment is recommended by an ophthalmologist, until resolution to Grade 1. Subsequently, the participant should be followed with ocular exam (slit lamp and visual acuity) at each cycle until total resolution of the event.
- Photographs of the cornea are recommended to be taken at the site, if possible, when ocular findings are first documented, and to follow progression when relevant. Tonometry and additional ocular assessment can be performed at the discretion of an ophthalmologist when applicable.

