8.2.6.3 Keratopathy/keratitis management

- Reversible non-inflammatory, microcystic keratopathy was identified as the dose limiting toxicity (DLT) during the dose escalation process in study TED13751with tusamitamab ravtansine. At slit-lamp examination, it presents as lesions consisting of 100s to 1000s microcysts and/or deposits that are initially observed at the periphery of the cornea, the limbus being preserved. The lesions have a centripetal distribution and evolve towards the center of the corneal upon resolution, following the natural keratinocyte regeneration process.
- For standardization of AE verbatim, keratopathy should be the preferred term unless otherwise specified by an ophthalmologist due to inflammatory findings on eye exams leading to a diagnosis of keratitis.
- The potential ocular/visual toxicity symptoms could include, but are not limited to, blurred vision, dry eye, and photophobia. Curative treatment may be used as recommended by an ophthalmologist.
- No primary prophylaxis other than prevention of dry eye with artificial tears and/or hyaluronic ophthalmic gel is recommended; the use of contact lenses is not permitted during the treatment period. Corticosteroid-containing ocular drugs are recommended for the management of keratopathy/keratitis in the case that ocular symptoms occur, and treatment will be performed based on discretion of ophthalmologist. Dose modification and recommendations are further described in Appendix 6 (Section 10.6).
- After resuming study treatment, a patient who had Grade ≥2 keratopathy/keratitis should be followed with standard ocular exams (ie, slit lamp examination under dilatation and visual acuity) every 2 cycles, even if symptoms are no longer reported. If no event recurs during the next 4 cycles, then regular follow-up (ie, symptom assessment at each visit with standard ocular exam in case of any ocular sign/symptom) is applied.

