	Grade 3-4 eg, symptomatic bronchospasm, urticaria lesions covering >30% BSA, hypotension, angioedema.	Interrupt SAR408701 infusion and definitively discontinue SAR408701.	Give diphenhydramine 50 mg IV and/or dexamethasone 10 mg IV and/or epinephrine and any required treatment per Investigator judgment.
Ocular toxicity: Keratopathy/keratitis ^b associated with SAR408701	Grade 1 Asymptomatic, Corneal lesions only observed on routine ocular examination and not requiring topical treatment.	Next infusion of SAR408701 at the same dose, with or without cycle delay, depending on the recommendation from the ophthalmologist (nature and extent of the lesion).	Standard ocular examination is planned as recommended by the ophthalmologist.

Table 10 - Recommended Dose Modification or Discontinuation for SAR40870

Event	Symptoms severity (NCI-CTCAE v5.0)	Dose modification	Supportive care guidelines
	Grade 2 Symptomatic, moderate decrease in visual acuity (best corrected visual acuity 20/40 and better or 3 lines or less decreased vision from known baseline)	1 st episode: SAR408701 cycle delay until resolution to Grade 1 (asymptomatic) and restart SAR408701 at the same dose. 2 nd episode: delay cycle until resolution to Grade 1 (asymptomatic) and SAR408701 dose reduction.	Standard ocular examination weekly until resolution ^{c} . Start curative treatment per ophthalmologist recommendation. After resuming study treatment, participant should be followed with standard ocular examination by every 2 cycles, even asymptomatic during next four cycles. If no recurrence, standard process with follow-up with ocular symptom is resumed. Management of study drug and follow-up process upon recurrence
	Grade 3 Symptomatic with marked decrease in visual acuity (best corrected visual acuity worse than 20/40 or more than 3 lines of decreased vision from known baseline, up to 20/200); corneal ulcer; limiting self-care ADL.	1 st episode: SAR408701 cycle delay until resolution (asymptomatic) and restart SAR408701 with dose reduction. 2 nd episode: definitive discontinuation of SAR408701.	to be discussed according to Grade of the event at recurrence, clinical benefit from study drug and recommendation from the ophthalmologist.

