Corneal events	CMQ "Corneal events compound level" containing the PTs included in both SOC "Eye disorders" and SMQ "Corneal disorders" (Narrow)	
Ocular/visual adverse events (excluding corneal disorders)	CMQ "Eye disorders exclude corneal disorders" containing PTs included in SOC "Eyes disorders" and excluding PTs in SMQ "Corneal disorders" (Narrow)	
Cardiac conduction defects	SMQ "Conduction defects" (Narrow)	

Table 6 - Selections for AESIs and other AEs of interest
--

Property of the Sanofi group - strictly confidential

AESIs and other AEs of interest	Selection
Peripheral neuropathy events	SMQ "Peripheral neuropathy" (Narrow and Broad)
Colitis events (excluding infective)	CMQ "Colitis (excluding infective)" containing PTs included in HLT "Colitis (excl infective)"
Hypersensitivity events	SMQ "Hypersensitivity" (Narrow) and defined as events occurring on the day or the day after the infusion
Hepatic disorders adverse events	SMQ "Hepatic Disorders" (Narrow and Broad)
Hematological adverse events	SMQ "Haematopoietic cytopenias" (Narrow and Broad)
AE related to COVID-19 illness	SMQ "COVID-19" (Narrow)

An overview of corneal TEAE will be provided with the following AE categories: any corneal TEAE, Grade \geq 3 corneal TEAE, treatment-emergent corneal SAE, corneal TEAE related to IMP, Grade \geq 3 corneal TEAE related to IMP, corneal TEAE leading to treatment discontinuation, and corneal TEAE leading to dose modification (cycle delay or dose reduction). In addition, a summary table of corneal events will be displayed by grade. A summary of treatment-emergent corneal events will be provided.

- Cycle of first onset of corneal event regardless of the grade
- Cycle of first onset of corneal event with the worst grade
- Number (%) of participants by worst grade
- Relationship to the study intervention: in case of multiple events with different relationships, if any event is related, then the relationship will be considered as related
- Action taken with the study intervention: in case of multiple events with different actions, the most severe action taken will be tabulated and selected according to the following order of severity: drug withdrawn, dose reduced and delayed, dose reduced, dose delayed, drug interrupted, dose not changed

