- Outcome: in case of multiple events with different outcomes, the most severe outcome will be tabulated and selected according to the following order of severity: fatal, not recovered or resolved, recovering or resolving, recovered or resolved with sequelae, recovered or resolved, unknown

In addition, analyses on occurrence and recurrence of corneal events will be provided. An occurrence of corneal event is defined as one or a group of concomitant corneal events. A recurrence is defined as any new occurrence of corneal event starting after a previous resolved occurrence.

- The number of occurrences by participant
- The time to first onset of corneal event will be described using Kaplan-Meier curves. Time to first onset is defined as the time from the date of first IMP administration to the date of the first occurrence of the event. In the absence of an event before the analysis cut-off date, it will be censored at the end date of the treatment-emergent period, analysis cut-off date or date of death, whichever occurs first.

- The time to recovery will be summarized using descriptive statistics in participants who had had at least one recovered or resolved occurrence of corneal event (with or without sequelae), considering the longest duration among all occurrences by participant.
- The time to recurrence will be summarized using descriptive statistics in participants who had had at least one recurrence, considering the shortest time among all recurrences by participant.

Besides the AE categorized as ocular/visual adverse events, all ocular/visual symptoms (coded term) recorded in e-CRF as associated symptom of the reported ocular treatment-emergent adverse events will be reported as descriptive analysis. Same analysis will be done separately for ocular/visual symptoms associated to corneal TEAEs (CMQ)."

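### The SAP's all-grade time to first corneal event measures first detection, not onset: eye exams between screening and EOT are mainly symptom-triggered, so early incidence is understated

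*Protocol*

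**What the plan says.** **Examination schedule.** Protocol Section 8.2.2 states: "Specific ocular tests performed by the ophthalmologist at screening, at EOT, and whenever indicated will include" visual acuity, slit lamp and Schirmer's test. The flow chart in Section 1.3.1 agrees: "at screening, EOT and whenever clinically indicated". Section 8.2.6.2 spells out the on-treatment trigger: "as required during the treatment (ie, on occurrence of ocular symptoms such as blurred vision, photophobia, pain), at the EOT visit". The check before each infusion is an enquiry about symptoms by the Investigator, not an eye examination. The one on-treatment series done without symptoms follows an earlier event (Section 8.2.6.3): "a patient who had Grade ≥2 keratopathy/keratitis should be followed with standard ocular exams".

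**Grade 1.** Table 10 (Protocol Section 10.6) describes Grade 1 keratopathy as asymptomatic: "Corneal lesions only observed on routine ocular examination and not requiring topical treatment". Grade 2 and above are described as symptomatic, apart from a Grade 4 entry that is defined by perforation or visual acuity.

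**Analysis.** SAP Section 3.6.2 lists "Cycle of first onset of corneal event regardless of the grade" and adds: "The time to first onset of corneal event will be described using Kaplan-Meier curves". Time runs from first dose to the date of the first occurrence. Participants without an event are right-censored at the end of the treatment-emergent period, the analysis cut-off or death, whichever is first. The Kaplan-Meier analysis has no grade restriction. Neither document distinguishes date of detection from date of onset.

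**The concern.** A Kaplan-Meier curve of time to onset needs an event date close to when the event began. For symptomatic events the symptom brings the participant to the ophthalmologist, so the date is roughly right. For a lesion without symptoms, the date depends on when someone next looks, and the next scheduled look is at EOT. The curve then mixes two kinds of date, one of which reflects when treatment stopped.

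Protocol Section 2.3.1 names corneal toxicity as the main anticipated risk, and the SAP gives it dedicated onset, recovery and recurrence summaries. If the all-grade curve is read as onset, corneal events will look rarer in the first cycles than they are, and some will look late only because of the exam schedule.

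**Working it through.** **1. Figures from the documents.** Corneal events at 100 mg/m² Q2W in the first-in-human study (Protocol Table 1): 56/186 = 30.1%, which reproduces. For 38 treated participants, 38 × 56/186 = 11.4, so about 11 events are expected. Median treatment is 24 weeks (Protocol synopsis). EOT is 30 ± 5 days after the last dose. The treatment-emergent period ends 30 days after the last dose (SAP Section 3.1).

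**2. What can happen to a first Grade 1 lesion.**
- It resolves before EOT: not recorded.
- It becomes symptomatic: dated at the triggered exam, later than it began.
- It persists to EOT: dated at EOT.
- An exam done for another clinical reason finds it earlier: dated closer to onset.

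The exams after a Grade 2 or higher event cannot date a first event.

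**3. One participant.** With 24 weeks of treatment, a lesion starting at week 6 and persisting is first seen at 24 + 30/7 = 28.3 weeks, a delay of 22.3 weeks.

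**4. EOT window.** Days 31 to 35 are allowed for the visit but lie outside the treatment-emergent period. That is 5 of the 11 days from 25 to 35, or 45% if all days are equally likely. A lesion first seen then is post-treatment, and the curve censors the participant.

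**5. Illustration by simulation.** Assumptions: treatment duration exponential with median 24 weeks; EOT exam at 30 days; 40% susceptible; onset uniform over weeks 3 to 12; asymptomatic lesions found only at EOT. This gives about 36% with any event. The asymptomatic share is varied because the documents do not give it.

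No resolution before EOT:

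| Asymptomatic share | Week-12 incidence, true | Week-12 incidence, recorded | Mean onset, true (weeks) | Mean onset, recorded (weeks) |
|---|---|---|---|---|
| 30% | 40% | 29% | 7.3 | 17.7 |
| 50% | 40% | 22% | 7.3 | 24.7 |
| 70% | 40% | 15% | 7.3 | 31.6 |

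A hand check on incidence is true × (1 − asymptomatic share): 40% × 0.7 = 28%, 40% × 0.5 = 20%, 40% × 0.3 = 12%. The simulated values are slightly higher because some participants reach EOT before week 12.

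**6. Allowing lesions to resolve.** At 50% asymptomatic, with exponential lesion duration (also assumed):

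| Mean lesion duration | Mean recorded onset (weeks) |
|---|---|
| No resolution | 24.8 |
| 24 weeks | 11.5 |
| 12 weeks | 9.1 |
| 6 weeks | 8.0 |

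The no-resolution value differs from step 5 only by simulation error; its median is 11.1 weeks. Recorded week-12 incidence stays near 22% against 40% true. At 70% asymptomatic with resolution it falls to about 14%. The delay in recorded onset therefore depends heavily on lesion duration, while the shortfall in early incidence hardly does.

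**7. Cross-check with another onset model.** True incidence 30.1%, lognormal onset (median 6 weeks, log-SD 0.6), no resolution, all EOT findings counted. Week-12 incidence is 29% true against 23%, 17% and 11% recorded with 25%, 50% and 75% asymptomatic. The direction is the same.

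**The case against.** The strongest objection concerns the late dating. A reader might infer that every asymptomatic first event is dated at EOT, so that the curve must show a strongly late-onset toxicity. The documents do not support that. Protocol Sections 2.3.1 and 8.2.6.3 describe the keratopathy as reversible; a lesion that clears before EOT is lost, not dated late. Step 6 shows most of the shift in mean onset disappearing once lesions can resolve. This stands, and it is why no single figure for the delay should be quoted. It does not remove the understated early incidence.

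Second, exams are allowed whenever clinically indicated, the corneal query covers more than keratopathy, and the general grading text in Protocol Section 10.3.3 lets a mild event carry mild symptoms. Some Grade 1 events will be found and properly dated during treatment. This also stands. A reader might conclude that the all-grade curve should be dropped for a Grade 2 or higher curve, but that would discard those events.

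Third, the SAP already tabulates corneal events by grade and gives the cycle of first onset at worst grade. This helps only in part: for a participant whose worst grade is 1, that cycle is still a detection date, and no time-to-onset curve is given for symptomatic events.

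Finally, interval censoring might seem required. For a participant with no exam after screening, the interval runs from screening to EOT, which is nearly the whole exposure. With about 11 events expected, and only some found at EOT, it would add little.

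**Conclusion.** The point holds as one of detection against onset. Followed as written, the SAP understates early all-grade corneal incidence and places EOT-found lesions as late steps. Under the assumptions in step 5, with 30% to 70% of events asymptomatic, recorded week-12 incidence is about 29% to 14% against 40% true. Mean recorded onset ranges from about 8 weeks (mean lesion duration 6 weeks) to 18–32 weeks (no resolution), against 7.3 true.

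These are illustrations. Susceptibility, the onset distribution, the asymptomatic share and lesion duration are all assumed. Table 1 mentions cohorts with only Grade 1 keratopathy/keratitis, but these are the loading-dose and every-3-weeks cohorts, and the remark sits in the neuropathy row, so it does not supply a share for this regimen. The safety analysis is descriptive; no test, sample size, interim rule or primary result is affected.

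**What to change.** In SAP Section 3.6.2:

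1. Add cycle of first onset and a Kaplan-Meier curve for symptomatic (Grade 2 or higher) corneal events, and use these to describe onset timing.
2. Keep the all-grade curve, label it *time to first detection*, and flag events first found at the EOT exam.
3. Report Grade 1 lesions first found at EOT as a proportion of participants examined at EOT. Include exams on days 31 to 35, and state that these fall outside the treatment-emergent period.

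Interval censoring of EOT-found events is optional.

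The cost is one extra curve and one table from data already collected. The Grade 2 or higher curve will rest on few events. No extra eye exams and no change to clinical management are involved.

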8.2.3 Vital signs

- Temperature, pulse rate, and blood pressure will be assessed.
- Blood pressure and pulse measurements will be assessed with a completely automated device, unless an automated device is not available.
- Blood pressure and pulse measurements should be preceded by at least 5 minutes of rest for the participant in a quiet setting without distractions (eg, television, cell phones).
- Vital signs (to be taken before blood collection for laboratory tests) will consist of 1 pulse and 3 blood pressure measurements (3 consecutive blood pressure readings will be recorded at intervals of at least 1 minute). The average of the 3 blood pressure readings will be recorded.

8.2.4 Electrocardiograms

- Single 12-lead ECG(s) will be obtained as outlined in the SoA (see Section 1.3) using an ECG machine that automatically calculates the heart rate and measures PR, QRS, and QT intervals.
- ECG can be performed on the same day before the study intervention administration or on the day before when requested on Day 1 pre-infusion. An ECG is to be repeated as clinically indicated.
- ECGs will be interpreted by a qualified physician at the site as soon after the time of ECG collection as possible, and ideally while the patient is still present, should additional ECGs be performed or for immediate patient management should any clinically relevant findings be identified.

